## 9.7 Selection of Doses in the Study

Doses of 100 mg, 200 mg, or 400 mg twice daily will be administered in this study. These doses were found to be safe and well tolerated in a phase 1 study of adolescents with ADHD.

Previous PK studies in both healthy adults (aged 26 to 48 years) and young adults (aged 20 to 32 years) showed an elimination half-life (t½) of about 4 hours. In view of the short half-life, twice daily dosing is expected to provide a more consistent pharmacologic effect throughout the day.

Administration of single oral doses of 100 mg NFC-1 after a meal to young adults (aged 20 to 32 years) showed rapid absorption (time to maximum plasma concentration [ $T_{max}$ ] from 0.6 to 1.5 hours), dose-proportional increases in exposure, and a  $t_{1/2}$  of 3.7 to 4.4 hours in healthy male adults. Comparison of doses administered under fed and fasted conditions to healthy male adults showed that food caused slower absorption ( $T_{max}$  of 1.5 versus 0.7 hours) and decreased the maximum observed plasma concentration ( $C_{max}$ ) (4.14 versus 5.65  $\mu$ g/mL), but no difference in the area under the plasma concentration-time curve extrapolated from time 0 to infinity ( $AUC_{0-\infty}$ ) (29.3 versus 31.3  $\mu$ g h/mL) and  $t_{1/2}$  (4.2 versus 4.3 hours). In separate studies, similar PK parameters were obtained following administration of 100 mg NFC-1 to healthy male adults and young adults, respectively, with  $T_{max}$  of 1.0 versus 1.2 hours,  $C_{max}$  of 2.57 versus 2.14  $\mu$ g/mL,  $AUC_{0-\infty}$  of 17.0 versus 14.0  $\mu$ g h/mL, and  $t_{1/2}$  of 4.4 versus 4.4 hours.

Preliminary evaluation of PK data from the recent adolescent PK study is consistent with previous PK data and demonstrated a linear dose/concentration profile with a t1/2 of approximately 4 hours.

#### 9.8 Selection of Timing of Dose for Each Subject

NFC-1 or matching placebo is to be taken orally twice daily during the treatment period (in the morning upon awakening [7:00 a.m.to 9:00 a.m.] and in the mid-afternoon [between 3:00 p.m.to 5:00 p.m.]) and can be taken in the fed or fasting state.

#### 9.9 Dose Adjustment Criteria

The duration of the dose-optimization period is 4 weeks to allow for up-titration to the highest dose and no more than one down-titration to the previous dose, if necessary.

Subjects will be instructed to take NFC-1 or placebo each morning upon awakening (at 7:00 a.m. to 9:00 a.m.) and in the mid-afternoon (3:00 p.m. to 5:00 p.m.). On Day 1, all subjects will begin taking NFC-1 or placebo and will be evaluated after 7 days ( $\pm$  2 days) for tolerability and effectiveness. Subjects may be titrated weekly to the next available dose strength after 7 days ( $\pm$  2 days) on the previous dose, based on the overall response of the subject. Additionally, if needed, a subject may be down-titrated to the previous dose level in order to optimize tolerability and efficacy. Subject response will be categorized by the investigator as 1 of 3 conditions and associated actions, with titration continuing until an "acceptable response" is achieved. These conditions are defined as follows:

Intolerable response (ie, intolerable side effects): Requires the subject to be tapered to a lower dose of NFC-1 (if available). However, if this lower dose produces an intolerable response as well, the subject should be discontinued from the study.

Ineffective response: The subject is not showing a significant reduction in symptoms, and requires increasing titration of NFC-1 to the next available dose strength, provided tolerability is acceptable, followed by weekly evaluation.

Acceptable response: A response is defined as acceptable if it shows a significant reduction in symptoms with tolerable side effects. Subjects categorized as "acceptable" may be maintained at their current dose for the remainder of the optimization period. Subjects who are tolerating study medication at the highest available dose but do not achieve an acceptable response should continue in the trial at that dose.

Further, if the "acceptable" dose is well tolerated and, in the opinion of the investigator, the subject would potentially receive additional symptom reduction, the dose may be increased to the next higher dose level.

If the subject experiences unacceptable intolerability, in the opinion of the investigator, the dose may be reduced (if available) by 1 dose level (to the previous dose). If the subject tolerates the dose reduction well and maintains symptom control, the subject may be maintained at that reduced dose for the remainder of the optimization period (through Visit 6).

Only 1 dose reduction is permitted during the optimization period. Visit 5 will be the last visit at which titration can occur. Once a subject has reached an optimal dose, this dose will be maintained for the remainder of the dose-optimization phase of the study (through Visit 6). Subjects who are unable to tolerate the IP will be discontinued. After the dose optimization period, subjects will continue to receive the current optimized dose of IP for an additional 2 weeks. A 7-day follow-up call will occur after discontinuing study treatment.

Subjects who discontinue because they are unable to tolerate the IP must complete all early termination (ET) visit assessments required during the last study visit. These subjects will also receive a 7-day follow-up call after discontinuing study treatment.

## 9.10 Drug Accountability

The investigator must maintain adequate records showing the receipt, dispensing, return, or other disposition of the IP including the date, quantity, batch or code number, and identification of subjects (subject number and initials) who received the IP. The investigator will not supply the IP to any person except those named as subinvestigators on the US Food and Drug Administration (FDA) Form FDA 1572, designated study personnel, and subjects in this study. The investigator will not dispense the IP from any study sites other than those listed on Form FDA 1572. IP(s) may not be relabeled or reassigned for use by other subjects. If any of the IP is not dispensed; is lost, stolen, spilled, unusable, or is received in a damaged container, this information must be documented and reported to Medgenics and appropriate regulatory agencies, as required.

Upon completion of the study, the IP (partly used, unused, and empty packaging [eg, bottles]) must be left in the original packaging and returned to the sponsor or designee for destruction.

## 9.11 Treatment Compliance

Treatment compliance with IP regimens will be assessed by study personnel via capsule counts of returned medication and by questioning the subject, if necessary, at every post-baseline visit. A subject who is not compliant (taken < 80% or > 100% of IP) will be counseled at each visit on

Version: Final Version v4.0 Page 27 of 58

the importance of taking IP as instructed. A subject who is noncompliant on 3 consecutive visits will be discharged from the study.

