## 8.3 Premature Subject Withdrawal

All subjects will be advised that they are free to withdraw from participation in this study at any time, for any reason, and without prejudice. Every reasonable attempt should be made by the investigator to keep subjects in the study; however, subjects must be withdrawn from the study if they withdraw consent to participate. Investigators must attempt to contact subjects who fail to attend scheduled visits by telephone or other means to exclude the possibility of an AE being the cause of withdrawal. Should this be the cause, the AE must be documented, reported, and followed as described in Section 11.2.

The sponsor reserves the right to request the withdrawal of a subject due to protocol violations or other reasons.

The investigator also has the right to withdraw subjects from the study at any time for lack of therapeutic effect that is intolerable or otherwise unacceptable to the subject, for intolerable or unacceptable AEs, intercurrent illness, noncompliance with study procedures, administrative reasons, or in the investigator's opinion, to protect the subject's best interest.

If a subject is withdrawn before completing the study, the reason for withdrawal and the date of discontinuation will be recorded on the appropriate electronic case report form (eCRF). Whenever possible and reasonable, the evaluations that were to be conducted at the completion of the study should be performed at the time of premature discontinuation.

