#### 9. TREATMENTS

## 9.1 Identification of Investigational Product(s)

The following IPs will be used in this study:

- NFC-1 will be provided as white opaque size-2 capsules containing 100 mg or 200 mg NFC-1; no excipients are used.
- Dose, route, and frequency (NFC-1): 100 mg, 200 mg, and 400 mg administered orally twice daily in the fed or fasting state.
- Matching placebo will be provided as white opaque size-2 capsules containing microcellulose instead of NFC-1.
- Dose, route, and frequency: Placebo for 100 mg, 200 mg, and 400 mg administered orally twice daily in the fed or fasting state.

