# 10.1.3.2 Dose Maintenance Phase (Visit 7, Day 35 [± 2 days], Visit 8, Day 42 [± 2 days], or Early Termination) Evaluation

At Day 35 and Day 42 or ET of the study, the following procedures will be performed:

- 1. Perform a physical examination and measure height (at Visit 8/ET only).
- 2. Measure vital signs (resting blood pressure, heart rate, and respiratory rate) and weight.
- 3. Collect blood and urine for clinical laboratory tests: hematology, serum chemistry, and urinalysis (at Visit 8/ET only).
- 4. Perform 12-lead ECG.
- 5. Perform a urine pregnancy test (for females of childbearing potential only).

- 6. Conduct ADHD-RS-5 evaluation.
- 7. Conduct CGI-S evaluation (at Visit 8/ET only).
- 8. Conduct CGI-I evaluation.
- 9. Conduct ASHS evaluation (at Visit 8/ET only).
- 10. Conduct SCARED evaluation (at Visit 8/ET only).
- 11. Conduct C-SSRS evaluation.
- 12. Access IWRS.
- 13. Subject returns unused IP.
- 14. Assess subject compliance using returned IP.
- 15. Assess and record concomitant medication and newly occurring AEs since the last evaluation.

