7.2 Protocol Deviations

Protocol deviations will be collected by the clinical team and provided to biostatistics prior to database lock. Protocol deviations will be reviewed and on a case-by-case basis to be classified and minor or major by the project team prior to database lock.

The categories of protocol deviations which will be reviewed and classified as major/minor include:

- Informed Consent/Assent
- Inclusion/Exclusion Criteria
- Concomitant Medication
- Use of prohibited medication
- Laboratory Assessment
- Study Assessments/Procedures
- Investigational Product
- Overdose/Misuse
- Visit Window
- Non-compliance
- Other

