^[2] A subject is non-compliant if they take < 80% or > 100% of IP. Compliance (Overall) = (sum of (Individual Week Compliance) * (Time-Weight)) * 100. Individual Week Compliance is defined as the number of capsules taken at a particular week divided by the expected number of capsules taken at a particular week. Given that a subject will be dose optimized, the number of expected capsules will vary according to which dose the subject is currently on for each day. Time-Weight is the fraction of x/y where x is the number of days in the week the subject is expected to be on dose and is the whole treatment duration.

T:\Medgenics\NFC-1\ADHD-201\...\xxx.sas run on DDMMMYYYY at HH:MM on data extracted on DDMMMYYYY

Protocol: MDGN-NFC1-ADHD-201

Page 1 of x Final

Table 14.3.3.1 Summary of Clinical Laboratory Data: Clinical Chemistry by Randomized Treatment by Study Visit Safety Population

Analyte		
Visit	NFC-1	Placebo
Statistic	(N=xx)	(N=xx)
4. 1. (
<pre><analyte (unit)=""></analyte></pre>		
Baseline		
n	XX	XX
Mean	XX XX	XX XX
Standard Deviation	XX.XXX	XX XXX
Median	XX XX	XX XX
Minimum, Maximum	(x x, x x)	(x x, x x)
Visit 3		
n	XX	XX
Mean	XX XX	XX XX
Standard Deviation	XX.XXX	XX XXX
Median	XX XX	XX XX
Minimum, Maximum	(x x, x x)	(x x, x x)

{Continue for all scheduled post-baseline visits and all analytes. Start a new page for every additional analyte}

Source: Listing 16.2.7.1

Table 14.3.3.2 Summary of Clinical Laboratory Data: Hematology by Randomized Treatment by Study Visit Safety Population

{Similar shell as Table 14.3.3.1; Source: Listing 16.2.7.2}

Table 14.3.3.3 Summary of Clinical Laboratory Data: Urinalysis by Randomized Treatment by Study Visit Safety Population

{Similar shell as Table 14.3.3.1; Source: Listing 16.2.7.3}

Page 1 of x Final

Table 14.3.3.4
Shifts from Baseline of Clinical Laboratory Data: Clinical Chemistry by Randomized Treatment Safety Population

Analyte Visit [1]		NF (N=				Place (N=		
Category	Missing	Low	Normal	High	Missing	Low	Normal	High
<analyte (unit)=""></analyte>								
Visit 3								
Missing	xx(xx.x%)	xx (xx x%)	xx (xx.x%)	xx(xxx%)	xx (xx x%)	xx (xx x%)	xx (xx.x%)	xx (xx x%)
Low	xx (xx.x%)	xx (xx x%)	xx (xx.x%)	xx (xx x%)	xx (xx x%)	xx (xx x%)	xx (xx.x%)	xx (xx x%)
Normal	xx(xx.x%)	xx (xx x%)	xx (xx.x%)	xx (xx x%)	xx (xx x%)	xx (xx x%)	xx (xx.x%)	xx (xx x%)
High	xx (xx.x%)	xx (xx x%)	xx (xx.x%)	xx (xx x%)	xx (xx x%)	xx (xx x%)	xx (xx x%)	xx (xx x%)
Visit 4								

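### Protocol 9.11 discharges repeatedly noncompliant subjects from the study, not only from IP, so a score carried a nominal 7 to 21 days can replace an obtainable Visit 8 value in the primary analysis

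*Protocol*

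**What the plan says.** Protocol 9.11 checks compliance by capsule count at every post-baseline visit. It defines noncompliance and the first response together: "A subject who is not compliant (taken < 80% or > 100% of IP) will be counseled at each visit on" the importance of correct dosing. The next step is fixed: "A subject who is noncompliant on 3 consecutive visits will be discharged from the study". The section leaves no discretion, and the exit is from the study.

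Other sections already deal with noncompliance:

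- Protocol 8.3 is discretionary: "The investigator also has the right to withdraw subjects from the study at any time". Its grounds include noncompliance with study procedures and the subject's best interest. It also asks the investigator to make every reasonable effort to retain subjects.
- SAP 7.2 introduces its list with "The categories of protocol deviations which will be reviewed and classified as major/minor include". Non-compliance and overdose/misuse are both on the list. A major deviation removes the subject from the PP Population (SAP 5).

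At exit, where feasible, "the evaluations that were to be conducted at the completion of the study should be performed at the time of premature discontinuation" (Protocol 8.3). Protocol 10.1.3.2 says "At Day 35 and Day 42 or ET of the study, the following procedures will be performed", and ADHD-RS-5 is among those procedures. After that, only a telephone call on AEs and concomitant medication is planned (10.1.4). For anyone who leaves before Visit 8, SAP 8.1 substitutes the last treated ADHD-RS-5 in an ANCOVA on all randomized subjects.

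The upper compliance limit is not the same everywhere. The footnotes to SAP Table 14.3.2 and Listing 16.2.4.2 agree with the protocol: "A subject is non-compliant if they take < 80% or > 100% of IP". SAP 6.3 sets the limit at 120%. SAP 10 does not list this as a change.

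**The concern.** The primary endpoint is the change to Visit 8, on everyone randomized. A subject who takes IP irregularly but is willing to attend is removed by the protocol itself, and an earlier score stands in for the endpoint. The rule does not keep poor adherers out of the ITT comparison. It only changes which of their scores is used. Protocol 7.2 gives the 2-week maintenance period as the time for the drug effect to stabilize before the endpoint, and a discharged subject misses some or all of it.

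The trigger is also tight. One extra capsule in a week counts as noncompliance, so subjects who are nearly adherent can be caught.

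**Working it through.** **Plan's own figure.** Protocol 13.2 and SAP 5.1 assume an effect size of 0.7, two-sided alpha of 0.05, 90 enrolled and 80 completing, for about 90% power. For a two-sample t test with n per arm, the noncentrality is d × √(n/2) on 2n − 2 degrees of freedom.

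- n = 45: 0.7 × √22.5 = 3.32, power 90.7% (normal approximation 91.3%).
- n = 40: power 87.1% (normal approximation 87.9%).

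The stated figure is reproduced with all 90 subjects, which is also the set the primary analysis uses.

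**When discharge can occur.** Visits 3 to 8 fall on Days 7, 14, 21, 28, 35 and 42, each ± 2 days (Protocol 10.1.3.1, 10.1.3.2). Carry = 42 − day of the third consecutive noncompliant visit.

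| Noncompliant at | Discharge day | Nominal carry | With windows |
|---|---|---|---|
| Visits 3, 4, 5 | 21 | 42 − 21 = 21 days | 17 to 25 |
| Visits 4, 5, 6 | 28 | 42 − 28 = 14 days | 10 to 18 |
| Visits 5, 6, 7 | 35 | 42 − 35 = 7 days | 3 to 11 |
| Visits 6, 7, 8 | 42 | 0 days | none nominally |

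These figures assume that an ADHD-RS-5 is obtained at exit. If it is missed, the carry is longer.

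**What trips the rule.** IP is supplied as "capsules containing 100 mg or 200 mg NFC-1; no excipients are used" (Protocol 9.1). At 100 mg twice daily with one capsule per dose, a 7-day week is 14 capsules.

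- 11/14 = 78.6%: noncompliant.
- 12/14 = 85.7%: compliant.
- 15/14 = 107.1%: noncompliant under 9.11, but inside the 120% limit of SAP 6.3 (1.2 × 14 = 16.8 capsules).

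At 400 mg twice daily, assuming two 200 mg capsules per dose, a week is 28 capsules, and one extra gives 29/28 = 103.6%.

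**Illustrative size.** The documents give no count of 9.11 discharges. The 90 − 80 = 10 expected non-completers are from all causes and both arms. Assume a net excess of k discharges in one arm of 45, and a gap of g SD between the carried and the Visit 8 score. Shift in the treatment difference = k × g / 45.

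| k | g | Shift (SD) | Share of 0.7 |
|---|---|---|---|
| 1 | 0.25 | 0.0056 | 0.8% |
| 1 | 0.5 | 0.011 | 1.6% |
| 5 | 0.25 | 0.028 | 4.0% |
| 5 | 0.5 | 0.056 | 7.9% |

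With unit SD the standard error is √(2/45) = 0.211, so the shift is 0.0056/0.211 = 0.03 to 0.056/0.211 = 0.26 of one standard error. If the shift goes against NFC-1, d falls to 0.694 or 0.644 and power to 90.3% or 85.6%. As a stress case, let the carried score hold none of the effect (g = 0.7, k = 5): d = 0.7 − 5 × 0.7/45 = 0.622, power 83.1%. A shift the other way would enlarge the estimate instead.

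**The case against.** **A fixed stopping rule is a defensible conduct and safety choice.** These are adolescents, 400 mg twice daily is the top dose, there is no Data Safety Monitoring Board, and the SAP has an overdose/misuse deviation category. This stands as an argument for stopping IP. It does not require ending assessments.

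**The effect may be nil.** Three failures in a row are needed, with counseling each time, and the subject's last score already reflects three visits of poor adherence. Nothing in the documents supports a particular gap between that score and Visit 8. This stands, and it limits the claim to a loss of obtainable data.

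**Carried scores are not all early.** A reader might infer that every one precedes the settled dose. Protocol 9.9 makes Visit 5 the last titration visit, so Day 28 and Day 35 scores follow about 7 and 14 days on the final dose. Only a Day 21 score may come before it.

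**The plan already shows something of this.** SAP 8.1 repeats the ANCOVA at each visit, and Table 14.1.1 reports noncompliance exits by arm, so an imbalance would be visible. Protocol 13.4.3.2 also plans a repeated-measures model, though SAP 8 does not specify it. None of these supplies the missing Visit 8 score.

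**The 100%/120% mismatch is a separate matter.** Correct: SAP 6.3 applies its limit to overall time-weighted compliance and does not decide who is discharged. It is worth aligning because the SAP contradicts itself and the protocol.

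**Conclusion.** The point holds as a low-cost improvement to the design. As written, 9.11 and SAP 8.1 together give up the Visit 8 score of subjects who might have attended, with a nominal carry of 21, 14 or 7 days. The number affected is unknown and possibly zero, the effect is probably small, and no direction is established. The illustrated shifts rest wholly on assumed values of k and g. The upper end is unlikely, since k = 5 would need at least half of the 10 expected non-completers.

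A reader might infer that the primary result is biased or that power is materially lost. The documents do not support that, because they give neither a discharge rate nor a gap. Nor is this an argument against LOCF, which is a declared choice. A reader might also extend the point to intolerability exits under Protocol 9.9. There IP has to stop, an ET visit is mandatory, and any later score would be off drug, so no change is proposed.

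**What to change.** Replace the last sentence of Protocol 9.11 with wording such as:

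> *After three noncompliant visits in a row, the subject is counseled again and a protocol deviation is recorded. The investigator, with the medical monitor, decides whether IP continues or stops; IP stops for repeated intake above the prescribed amount if there is a safety concern. Unless consent is withdrawn, scheduled visits and ADHD-RS-5 assessments continue to Visit 8.*

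In the analysis:

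- Subjects still on IP contribute their observed Visit 8 score.
- For subjects whose IP is stopped, the last treated value stays primary and the observed Day 42 score is supportive. SAP 8.1 is worded around leaving the study, so add a clause covering subjects who stop IP but stay.
- PP membership stays with the SAP 7.2 review.

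Use one upper limit, 100% or 120%, in Protocol 9.11, SAP 6.3 and the footnotes to Table 14.3.2 and Listing 16.2.4.2.

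The cost is one sentence in the protocol, a clause in SAP 8.1 and one aligned limit. No visit is added, because Visits 6 to 8 are already scheduled. The downside is that Visit 8 scores from poorly adherent subjects may slightly dilute the effect. Scores from subjects off IP need the last-dose date and any ADHD medication recorded to be interpretable.

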## 9.12 Permitted and Prohibited Therapies

All concomitant medications used (including over-the-counter [OTC] medications) will be recorded in the source document and on the appropriate eCRF.

## 9.12.1 Permitted Therapies

Ongoing behavioral therapies, including individual cognitive behavioral therapy, group cognitive behavioral therapy, social effectiveness training, ADHD behavioral therapy, or applied behavioral analysis are allowed and must be maintained at the same frequency/intensity as at Screening. The initiation of new behavioral therapies is not allowed.

The use of inhaled bronchodilators is allowed, if needed. Antibiotics and OTC medications that do not affect blood pressure, heart rate, or the central nervous system, which are considered necessary for the subject's welfare, may be administered at the discretion of the investigator. The administration of all such medication must be recorded in the appropriate section of the source documentation and eCRF. Non-sedating antihistamines such as Allegra® are allowed, as are OTC non-stimulant cold remedies such as guaifenesin.

The use of inhaled steroids (corticosteroids) for asthma is allowed.

## 9.12.2 Prohibited Therapies

All ADHD medications will be discontinued prior to starting this study. There will be a washout phase of 5 days for stimulants and 14 days for atomoxetine and noradrenergic agonists. Study subjects will not start any new ADHD medication during the study. Due to their potential to interfere with safety, efficacy, or tolerability assessments, the following medications are prohibited during the study:

- Any medication which is a substrate of CYP3A4, CYP2B6 or CYP2D6.
- Norepinephrine reuptake inhibitors.
- Anxiolytic or sedative hypnotic medications.
- Antidepressants, tricyclic antidepressants, selective serotonin reuptake inhibitors (SSRI), selective norepinephrine reuptake inhibitors including atomoxetine (Strattera).
- Clonidine.
- Guanfacine.
- Mood stabilizers (including lithium, anticonvulsants, and antipsychotics).
- Antihypertensive agents.
- Psychostimulants.
- Sedating antihistamines.
- Investigational compounds.
- All herbal preparations.
- Cough/cold preparations containing stimulants.

Subjects receiving excluded therapies will be ineligible for study enrollment or for continuation in the study, at the discretion of the investigator and sponsor.

